This will be a prospective study conducted in cohorts of patients with CAD on treatment per standard of care with DAPT for at least 6 months after elective PCI and 12 months after an ACS. Patients treated with either aspirin (81mg/qd) plus clopidogrel, aspirin (81mg/qd) plus ticagrelor (90mg/bid), or aspirin (81mg/qd) plus prasugrel (10mg/bid) will be identified. The study will be performed at the Division of Cardiology of University of Florida Health, Jacksonville, Florida. Patients will be recruited in the Cardiology Clinics of our institution and will be screened by Cardiology Research staff, who will verify that all candidates meet inclusion and exclusion criteria. Results from blood tests performed within the last 90 days will be considered valid for screening purposes. If these are not available, a blood sample will be collected for the screening phase.

After providing written informed consent, each cohort will be randomized to either maintain DAPT or to DPI. DPI consists in treatment with aspirin (81mg/qd) plus rivaroxaban (2.5mg/bid). Patients randomized to DAPT will continue the guideline recommended DAPT regimens. Therefore, in adjunct to low-dose aspirin (81mg), clopidogrel (75mg/qd) and prasugrel (10mg/qd) will be maintained at the same dosing regimen, while ticagrelor dosing will be reduced from 90mg/bid to 60mg/bid. Randomized treatment will be maintained for 30 ± 3 days. PD assessments will be conducted at 3 time points: i) baseline (while on standard of care DAPT therapy) before the administration of the morning doses of antiplatelet therapy; ii) 30 ± 3 days after randomization before the administration of the morning doses of antithrombotic therapy (trough levels); iii) 30 ± 3 days after randomization 2 hours after the administration of the

morning doses of antithrombotic therapy (peak levels). Figure 1 illustrates the overall study design.

Figure 1. Study design

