- Systemic treatment with strong inhibitors of both CYP 3A4 and p-glycoprotein (e.g., systemic azole antimycotics, such as ketoconazole, and human immunodeficiency virus [HIV]-protease inhibitors, such as ritonavir), or strong inducers of CYP 3A4, i.e. rifampicin, rifabutin, phenobarbital, phenytoin, and carbamazepine
- Any known hepatic disease associated with coagulopathy
- Subjects who are pregnant, breastfeeding, or are of childbearing potential, and sexually active and not practicing an effective method of birth control (e.g. surgically sterile, prescription oral contraceptives, contraceptive injections, intrauterine device, double barrier method, contraceptive patch, male partner sterilization)
- Concomitant participation in another study with investigational drug
- Known contraindication to any study related procedures
- Hemoglobin ≤ 9 mg/dL
- Platelet count $<80 \times 10^6$ /mL

Laboratory assessments

Peripheral venous blood samples will be drawn through a short venous catheter inserted into a forearm vein and collected in citrate, EDTA, and serum tubes as appropriate for assessments. The first 2-4 mL of blood will be discarded to avoid spontaneous platelet activation. Blood sampling for PD will be performed at 3 time points as described above and shown in the study design section. The following tests will be performed to explore platelet aggregation, thrombin generation, and thrombus formation

1. VerifyNow PRU
2. Light Transmittance Aggregometry (LTA)
3. Thrombelastograph Coagulation Analyzer TEG 6s Series system
4. Thrombin Generation

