Laboratory assessments including VerifyNow PRU, LTA, and TEG will be performed within 30-60 minutes of sample collection. Thrombin generation assessments will be performed on stored samples as final batch analysis. Samples will be stored under required refrigerated conditions at the Thrombosis Research Laboratory of the Cardiovascular Research Department of the University of Florida-Jacksonville. Only laboratory staff will have access to the samples. Subject identity will be protected. In particular, samples will be de-identified and data coded. This information will be stored in locked filing cabinets or in computers with security passwords. All laboratory assessments with the exception of thrombin generation measures will be performed at the Thrombosis Research Laboratory of the Cardiovascular Research Department of the University of Florida-Jacksonville. Thrombin generation assessments will be performed at CirQuest laboratories in Memphis, TN ([name]). Blood samples will also be stored for further future assessments of markers of thrombosis and inflammation.

Description of laboratory assays

1) VerifyNow (VN) PRU: The VN System is a turbidimetric based optical detection system which measures platelet induced aggregation as an increase in light transmittance (Accumetrics, San Diego, CA) and will be utilized according to manufacturer's instructions, as previously described [8]. The assay is based on microbead agglutination and uses specific reagents for the pathways of interest. The VN-PRU assay, by combining ADP+PGE1, measures changes in platelet function specific to P2Y₁₂ receptor inhibitors. The assay is based upon the ability of activated platelets to bind fibrinogen. Fibrinogen-coated microparticles aggregate in proportion to the number of GP IIb/IIIa receptors expressed. Light transmittance increases as activated

platelets bind and aggregate fibrinogen-coated beads. The instrument measures this change in optical signal and reports results in P2Y₁₂ Reaction Units (PRU).

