4) Thrombin Generation Assay: TGA assays will be performed using PPP samples prepared from the various treatment groups [10]. The TGA assay will be carried out using Technothrombin® fluorogenic assay kit (Diapharma) following manufacturer's recommended guidelines. Briefly, a reaction mix is prepared containing low or high amounts of TF and phospholipid micelles, plus the fluorogenic thrombin substrate (1 mM Z-G-G-R-AMC, 15 mM CaCl₂). Test samples will be analyzed in duplicate by adding the above prepared reaction mix to test samples at a 3:2 ratio in a 96-well plate. After addition of samples, plates will be incubated at 37°C in a water bath, and kinetics of thrombin generation will be recorded for 60 min at 1 min intervals using Synergy-2 fluorescence plate reader set at ~360 nm/~460 nm excitation/emission. Data will be recorded in BioTek's Gen 5 software and analyzed using BioTek FLx800 Gen 5_TGA Evaluation Software. Final results will be exported into Microsoft excel for data analysis.

Study endpoints and statistical analysis

The primary end point of our study will be the comparison of markers of platelet aggregation, thrombin generation, and thrombus formation between DAPT and low-dose rivaroxaban plus aspirin for each DAPT regimen at 30 days. Exploratory end points will include the intragroup comparison between aspirin plus ticagrelor 90 mg bid and low-dose rivaroxaban plus aspirin. Since there are no preliminary data exploring the PD effects of low-dose rivaroxaban in addition to aspirin and how this compare with DAPT, we arbitrarily chose a sample size of 90 patients (30 patients per cohort). This approach is in line with guidelines for pilot investigations [11].

For baseline characteristics, categorical variables will be expressed as frequencies and percentages; continuous variables will be presented as mean \pm SD or median [IQR]. Continuous variables will be analyzed for normal distribution with the Kolmogorov-Smirnov test. Comparisons for the primary end point as well as for other intergroup comparisons of continuous variables will be performed with an analysis of covariance with a general linear model with baseline value of the corresponding platelet function test as a covariate. Intragroup comparisons will be performed with paired sample t-test or Wilcoxon test. A p-value < 0.05 will be considered statistically significant. Statistical analysis will be performed with SPSS version 24 software (SPSS Inc.).

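### The primary end point names no marker, does not choose between the two day-30 samples and sets no multiplicity rule, so unadjusted testing at 0.05 can exceed a 5% error rate within a cohort

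*Combined protocol and SAP*

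**What the plan says.** The section Study endpoints and statistical analysis opens its definition of the primary end point with "The primary end point of our study will be the comparison of markers of platelet aggregation, thrombin generation, and thrombus formation between DAPT". The rest of that sentence gives the other side of the comparison and its timing: "low-dose rivaroxaban plus aspirin for each DAPT regimen at 30 days". It names three domains but no read-out within any of them. The analysis is an ANCOVA for each measure with its own baseline value as covariate, followed by the general rule "A p-value < 0.05 will be considered statistically significant".

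Under Study design, "each cohort will be randomized to either maintain DAPT or to DPI", and two of the three pharmacodynamic samples fall at day 30. One is the trough sample, "30 ± 3 days after randomization before the administration of the morning doses of antithrombotic therapy (trough levels"). The other is the peak sample, "30 ± 3 days after randomization 2 hours after the administration of the" morning doses. The end-point sentence does not say which of these it means.

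Laboratory assessments introduces the assays with "The following tests will be performed to explore platelet aggregation, thrombin generation, and thrombus formation", and the assay descriptions fix the panel in advance:

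- VerifyNow PRU, which "measures changes in platelet function specific to" P2Y12 receptor inhibitors.
- Light transmittance aggregometry with seven agonist conditions.
- TEG 6s, with five HKH parameters and three read-outs each for AA and ADP.
- Thrombin generation with low or high tissue factor and no named output parameter.

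No section ranks these measures, adjusts for their number, or says that p-values are to be read descriptively.

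**The concern.** A primary end point should fix, before the data are seen, which comparison carries the main conclusion. Here it is a class of comparisons. Each domain can be represented by more than one read-out or condition, and each read-out can be taken at trough or at peak. With every test judged at 0.05 and no rule for combining them, a report could present whichever marker crosses the threshold as the primary result and still comply with the plan.

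The assays themselves are prespecified, so the problem is mainly multiplicity, together with freedom over what to emphasise in reporting.

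A second difficulty is interpretive. The DPI arm takes no P2Y12 inhibitor, so a P2Y12-specific read-out such as PRU may differ between arms for that reason alone. That is a genuine difference between regimens, which is what the stated objective compares, but it is not an effect of rivaroxaban. The plan does not say how such a result bears on the primary conclusion.

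The section Possible benefits says that observed differences may prompt a larger clinical study, so a chance finding could influence what is done next.

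**Working it through.** **Inputs from the plan.** Threshold 0.05 per test, unadjusted. Three domains. Two day-30 samples. Three cohorts of 30, each randomized to two arms (3 × 30 = 90, as stated). The plan gives no power, effect size, SD or family-wise error rate, so it has no error figure to reproduce beyond the 0.05.

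**Assumptions not in the plan.** Two-sided tests; 1:1 allocation, hence 15 per arm; a common between-marker correlation from 0 to 0.9; and a rule that one significant marker counts as a primary difference.

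**Independent tests.** The chance of at least one false positive among k null tests is 1 − 0.95^k:

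- k = 2: 1 − 0.95² = 9.8%
- k = 3: 1 − 0.95³ = 14.3%
- k = 6: 1 − 0.95⁶ = 26.5%

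**Correlated tests.** Two-sample t-tests, 15 v 15, equal correlation between markers, 200,000 simulations per cell, rate per cohort:

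| Null tests in the cohort | corr. 0 | 0.5 | 0.7 | 0.9 |
|---|---|---|---|---|
| 3: one marker per domain, one time, no marker differs | 14.2% | 12.7% | 11.0% | 8.5% |
| 2: as above, but one domain truly differs | 9.8% | 9.2% | 8.5% | 7.1% |
| 6: one marker per domain at trough and peak | 26.3% | 21.1% | 16.8% | 11.1% |

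The top of the third row is a bound, because trough and peak values of the same marker will be correlated. At perfect correlation every row falls to 5%.

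**Check with the planned model.** ANCOVA with a baseline covariate (assumed baseline correlation 0.5) gives 14.2 / 12.5 / 11.2 / 8.6% for three null tests. Covariate adjustment does not remove the excess.

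**Effect of adjustment.** Bonferroni across three markers (0.05/3 = 0.0167 each) brings the per-cohort rate to 4.9 / 4.5 / 4.0 / 3.1%. When all three markers are null, Holm has the same rate, because its first step uses the same level.

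**Cost in power.** Noncentral t, 15 per arm, 27 residual degrees of freedom, 80% power, no gain from the covariate: the detectable difference is 1.06 SD at 0.05 and 1.25 SD at 0.0167.

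**The case against.** The strongest reply is that this is a pilot. Its aims are feasibility and comparing pharmacodynamic profiles, its tests are described as exploratory in purpose, and its sample size is openly arbitrary. A profile comparison may not need a single winning marker, and the plan never says that one significant result makes the study positive.

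Much of this stands. The any-one-marker rule is an assumption, so the rates are conditional on it. The profile aim is also a good reason to offer a descriptive reading as one of the remedies. However, the plan's references to pilot guidance support the sample size and the possible addition of patients; they do not make the analysis descriptive. The plan separates a primary end point from exploratory ones and applies a significance threshold.

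It is also fair to say that the scenario in which no marker differs is doubtful if a P2Y12-sensitive read-out represents aggregation. The two-null row then applies, at 7-10%. That is lower but still above 5%.

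A reader might go further and infer any of the following, which the documents do not support:

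- **That no day-30 sampling time is named.** Two are named, and the design explains that trough and peak are both taken to describe response to rivaroxaban. What is missing is the choice between them, or a statement that both count.
- **That error accumulates over all three cohorts**, for example 1 − 0.95⁹ = 37% for nine independent tests. The end point is stated for each regimen and randomization is within cohort, so three separate questions is the natural reading. The plan makes no claim that a result in any one cohort suffices.
- **That a rate can be given for the whole panel.** TEG alone has 5 + 6 = 11 listed read-outs and thrombin generation has no named parameter, so the number of tests is not determined.

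**Conclusion.** The concern holds as an omission within each cohort. The plan leaves the primary marker unnamed, the day-30 time unchosen and multiplicity unaddressed, while judging each test at 0.05. The text itself establishes those three gaps.

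The size is less certain. With one marker per domain at one time, the false-positive risk is about 8.5-14% per cohort if nothing differs and about 7-10% if one domain truly differs. It reaches at most about 26% if both times are tested. These figures rest on the assumed any-one-marker rule, 15 per arm and correlations between 0.9 and 0. They show what the stated threshold permits under those assumptions and are not an error rate that the plan itself implies. The point should be fixed before analysis; the pilot setting moderates its weight but does not remove it.

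**What to change.** Before analysis, amend Study endpoints and statistical analysis in one of three ways:

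1. Name one primary marker and one day-30 sampling time for each cohort.
2. Keep all three domains primary, naming one marker per domain at one day-30 time, with Holm adjustment across the three.
3. Declare the whole panel descriptive, with baseline-adjusted differences and 95% confidence intervals and no significance claim. This fits the pilot and profile aims.

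Under options 1 and 2, state that each cohort is a separate question at 0.05, and report all other markers and the other day-30 time as exploratory baseline-adjusted differences with 95% confidence intervals. Under any option, state that P2Y12-specific read-outs such as PRU reflect the difference between regimens and not an effect of rivaroxaban.

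The change is to wording only, with no added patients, samples or assays. The price is that fewer results can be called significant. Option 1 makes the other two domains exploratory. Option 2 raises the 80%-power detectable difference for the smallest p-value from 1.06 to 1.25 SD (15 per arm assumed, no covariate gain). Holding 1.06 SD at the stricter level would take about 21 per arm, or 21 × 2 × 3 = 126 patients. Because the plan allows patients to be added if the sample is judged too small, the investigators should say whether they accept the loss of power instead.
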